**Nova Laboratories Limited****CLINICAL TRIAL PROTOCOL****PRODUCT:** Oral Liquid 13-cis-retinoic acid (13-CRA)**PROTOCOL NUMBER:** INV500**VERSION NUMBER:** Version 5.0**DATE:** 08 Dec 2017**TITLE:** **Relative bioavailability and comparative pharmacokinetics of 13-CRA oral liquid and extracted capsule formulations: a randomised, open label, multi-dose, cross-over clinical trial in patients requiring treatment cycles of 13-CRA.****My-CRA (SHORT TITLE)****PHASE OF DEVELOPMENT:** Phase II**DEVELOPMENT:****TRIAL DESIGN:**

An open label, randomised, multiple dose, cross-over relative bioavailability and pharmacokinetics trial of oral 13-CRA liquid and extracted capsule formulations administered to patients from 0 months – < 21 years.

**TEST PRODUCT:**

1. Oral liquid formulation of 13-Cis Retinoic Acid – test product.  
2. Isotretinoin capsules (extracted per standard of care)– reference product.

The dose administered will be 200mg/m^2/day for both test and reference product. Patients with a body weight of ≤12kg will receive a dose of 160 mg/m^2.

**DURATION OF****TREATMENT:**

Two months.

**SYNOPSIS**

TITLE	Relative bioavailability and comparative pharmacokinetics of 13-CRA oral liquid and extracted capsule formulations: a randomised, open label, multi-dose, cross-over trial in patients requiring treatment cycles of 13-CRA.
TRIAL NUMBER:	INV500
FINAL PROTOCOL DATE:	Version 5.0 : Dated: 08 December 2017
PHASE:	II
SPONSOR:	Nova Laboratories Limited [name], UK
SENIOR CLINICAL ADVISORS PRINCIPAL INVESTIGATOR/ PLANNED TRIAL SITES: (Trial sites will be approved for initiation, full site initiation will take place when a suitable patients is identified)	[REDACTED]
TEST PRODUCT:	Oral liquid formulation of 13-Cis Retinoic Acid
REFERENCE PRODUCT:	Isotretinoin capsules (extracted per standard of care guidelines)
DOSE:	The dose administered will be 200mg/m  /day for both test and reference product. Patients with a body weight of ≤12kg will receive a dose of 160 mg/m  .
OBJECTIVES:	Primary objective: To determine the relative bioavailability and pharmacokinetics of 13-CRA administered as oral liquid and extracted capsule formulations. Secondary objectives: To determine the safety and tolerability. To assess palatability and acceptability.
TRIAL DESIGN:	An open label, randomised, multiple dose, cross-over relative bioavailability and pharmacokinetics trial of oral 13-CRA liquid and extracted capsule formulations administered to patients from 0 years – < 21 years.
SAMPLE SIZE:	Up to 20 patients, both male and female, aged 0 years to < 21 years of age will be recruited: A minimum of 4 subjects will be enrolled in the 0 to < 2 years age group and 4 subjects in the 2 to < 6 years age group.
INCLUSION CRITERIA:	
 
1. Male or female aged from 0 years to < 21 years of age.
 
2. Patient with high risk neuroblastoma, or unresectable, unfavourable histology intermediate risk neuroblastoma the latter age ≥ 18 months at diagnosis
 
3. Patient who is scheduled to receive at least two treatment cycles of 13-CRA.
 
4. Patient who cannot swallow 13-CRA capsules (i.e. requires extraction of 13-CRA from the capsules).
 
5. Negative pregnancy test for females of child-bearing potential no
 

	
more than seven days before initiation of treatment, and sexually active patients and partners agreeing to undertake adequate contraceptive measures (see section 4.5).
 
 
Provision of a single or double lumen central venous catheter for sampling (i.e. already in place).
 
Parent(s)/legal guardian able and willing to provide written informed consent for the patient to take part in the trial.
 
Where applicable, the patient should assent to undergo blood sampling for pharmacokinetic purposes and to allow physiological measurements to be made.
 
																													
EXCLUSION CRITERIA:	
 
Any clinically significant medical condition or abnormality, which, in the opinion of the investigator, might compromise the safety of the patient or which might interfere with the trial.
 
Diagnosis of high-risk neuroblastoma (HRNBL) which is currently being treated on the SIOPEN HRNBL trial (patients who have exited this trial will be eligible).
 
Known allergy to 13-CRA or any of the excipients.
 
Inadequate contraception measures in females of childbearing age.
 
Receiving concomitant treatment with tetracyclines.
 
																													
CRITERIA PRIOR TO STARTING EACH CYCLE OF 13-CIS-RA	
 
Total bilirubin <math>\leq 1.5 \times</math> normal, and (SGPT) ALT <math>\leq 5 \times</math> normal. Venocclusive disease if present, should be stable or improving.
 
Skin toxicity no greater than CTCAE Grade 1
 
Serum triglycerides <math>< 5.65 \text{ mmol/L}</math>.
 
No haematuria and / or proteinuria on urinalysis.
 
Serum calcium <math>\geq 2.0 \text{ mmol/L}</math> to <math>\leq 2.9 \text{ mmol/L}</math>.
 
Serum creatinine based on age / gender as follows: 
  
 Age	Maximum Serum Creatinine <math>\mu\text{mol/L}</math>	
 
 Male	Female	
   
 1 month to <math>< 6</math> months	35	35	
 
 6 months to <math>< 1</math> year	44	44	
 
 1 to <math>< 2</math> years	53	53	
 
 2 to <math>< 6</math> years	70	70	
 
 6 to <math>< 10</math> years	88	88	
 
 10 to <math>< 13</math> years	106	106	
 
 13 to <math>< 16</math> years	132	124	
 
 <math>\geq 16</math> years	150	124	
  
 
 
Patients with a seizure disorder must be well controlled and taking anticonvulsants. CNS toxicity <math>< \text{grade } 2</math> (CTCAE).
 
	Age	Maximum Serum Creatinine $\mu\text{mol/L}$		Male	Female	1 month to $< 6$ months	35	35	6 months to $< 1$ year	44	44	1 to $< 2$ years	53	53	2 to $< 6$ years	70	70	6 to $< 10$ years	88	88	10 to $< 13$ years	106	106	13 to $< 16$ years	132	124	$\geq 16$ years	150	124
Age	Maximum Serum Creatinine $\mu\text{mol/L}$																													
	Male	Female																												
1 month to $< 6$ months	35	35																												
6 months to $< 1$ year	44	44																												
1 to $< 2$ years	53	53																												
2 to $< 6$ years	70	70																												
6 to $< 10$ years	88	88																												
10 to $< 13$ years	106	106																												
13 to $< 16$ years	132	124																												
$\geq 16$ years	150	124																												
WITHDRAWAL CRITERIA:	
 
Positive pregnancy test - pregnancy testing will be undertaken no more than seven days before treatment commences and routinely no more than seven days before each course of treatment in females of childbearing potential. If a patient is found to be pregnant during the trial, the next course of treatment will not be given until the pregnancy has been discussed with the treating clinician, and the patient will be withdrawn from the trial whether or not treatment is continued.
 
Request of the patient, for any reason.
 
Discretion of the investigator.
 
																													
TREATMENT STRATEGY:	
All patients requiring at least two cycles of 13-CRA therapy will be eligible for recruitment into the trial.
 
13-CRA will be prescribed to patients according to local treatment protocols at each clinical site. The dose administered will be <math>200 \text{ mg/m}^2/\text{day}</math> for both test and reference product. Patients with a body weight of <math>\leq 12 \text{ kg}</math> will receive a dose of <math>160 \text{ mg/m}^2</math>.
 
The pharmacokinetics of 13-CRA liquid (test product) and extracted capsule (reference product) will be evaluated over two months. Prior
																													

	to the initiation of 13-CRA treatment as part of the trial, patients will be randomised to receive either liquid or capsule formulation in “My-CRA month 1”. The patients will then cross-over to the alternative formulation in “My-CRA month 2”. The patients on the trial who require further treatment will revert to standard therapy i.e. extracted capsules according to local practice.										
ENDPOINTS:	
Primary Endpoints: Pharmacokinetic parameters (13-CRA) Primary parameters:
 
 
• Relative bioavailability
 
• Clearance (CL/F),
 
• Volume of distribution (V/F)
 
 
Secondary parameters:
 
 
• Time to maximum concentration (<math>T_{max}</math>),
 
• Maximum plasma concentration (<math>C_{max}</math>),
 
• Area under plasma concentration time curve (AUC),
 
• Half-life (<math>t_{1/2}</math>)
 
• Levels of the metabolite 4-oxo-13-cis-RA.
 
 
Secondary Endpoints: Safety parameters
 
 
• Evaluate the local (oro-pharyngeal) tolerability
 
• Skin toxicity
 
• Hypercalcaemia
 
• Hepatotoxicity
 
• Triglycerides
 
 
Oro-pharyngeal adverse event data will be listed as adverse events and separately summarised.
 
Palatability and Acceptability: Evaluate the taste acceptability of the new oral liquid formulation of 13-CRA.
										
ADVERSE EVENTS	All adverse events that occur during the duration of therapy will be recorded and reports per regulatory health authority requirements. All serious adverse events (SAEs) will be followed until resolution or stabilisation.										
PROCEDURE	
It is anticipated that all patients recruited into the trial will have a central line in situ.
 
Patients will attend the site clinic on Pharmacokinetic Trial Days:
 
Month 1: Day 1 and Day 14 Month 2: Day 1 and Day 14
 
On the day of sampling, 13-CRA (reference or test) will be administered in the clinic by a research nurse. Blood (2 ml) will be sampled post-dose at time points selected as follows:
 
  
 Time point (h)	
   
 0.5 (Day 1 and Day 14)	
 
 1	
 
 1.5	
 
 *2	
 
 3	
 
 4	
 
 5	
 
 *6	
 
 **24-48 (Day 15 or 16)	
  
	Time point (h)	0.5 (Day 1 and Day 14)	1	1.5	*2	3	4	5	*6	**24-48 (Day 15 or 16)
Time point (h)											
0.5 (Day 1 and Day 14)											
1											
1.5											
*2											
3											
4											
5											
*6											
**24-48 (Day 15 or 16)											

	
*The 2 hour and 6 hour samples are mandatory, with at least three further samples (where possible) selected over 0.5 to 5 hours.
 
**Sample at 24-48 hours applies only to the final dose administered on Day 14 to allow the elimination phase of 13-CRA to be calculated. For individual patients sampling times should remain the same across each of the four PK days, where possible.

PATIENTS DURATION:	
Patients will be administered twice daily doses of 13-CRA for the duration of the trial. Evaluation of the test and reference product will occur over two months of therapy. Individual patient's participation will therefore be for 2 months. The whole trial recruitment period is estimated to be approximately 12 to 18 months from initiation.

STATISTICAL METHODS	
The data from all patients taking part in the trial will be pooled and analysed simultaneously to avoid excessive blood sampling. Population pharmacokinetic parameters will be estimated by using a non-linear, mixed effects modelling approach.
 
In the population approach all data from different individuals are fitted simultaneously using a non-linear, mixed effects modelling approach and post hoc individual kinetic parameters can be calculated with as few samples as one per individual. An appropriate software package such as NONMEM will be used to conduct the analysis.
 
Preliminary analyses will focus on the structural and variance models. One and two compartment models with first and zero order inputs will be implemented. Between patient variability will be assumed to be log-normally distributed, and residual error will be modelled using additive, proportional and combined error structures.
 
Adverse events will be coded according to the current version of MedDRA. Reporting of the safety data will be of a descriptive nature and presented using summary statistics.
 
Analysis will be planned and documented in the Statistical Analysis Plan.

Data Safety Monitoring Committee (DSMC)	
An independent Data Safety Monitoring Committee will be formed to alert and/or make recommendations to The Sponsor about any existing or potential safety issues.

**ABBREVIATIONS**

13-CRA	13-Cis Retinoic Acid
AE	Adverse event
AUC	Area under the plasma drug concentration-time curve extrapolated to infinity
AUC 0-24	Area under the plasma drug concentration-time curve from zero to 24 hours
C max	Maximum observed plasma concentration
CL/F	Apparent plasma clearance following intranasal administration
CRF	Case report form
CQC	Care Quality Commission
%CV	Coefficient of Variation calculated using $100 \times \sqrt{e^{s^2} - 1}$ , where $s^2$ is the variance of the log transformed data
FBC	Full blood count
GCP	Good clinical practice
GLP	Good laboratory practice
HRNBL	High Risk Neuroblastoma
HR-NBL-1.7/SIOPEN	current treatment trial for HRNBL
IEC	Independent ethics committee
IM	Intramuscular
IMP	Investigational medicinal product
IV	Intravenous
kg	kilogram
LFT's	Liver function tests
MHRA	Medicines & Healthcare products Regulatory Agency
ml	millilitre
NHS	National Health Service
NPSA	National Patient Safety Agency
PD	Pharmacodynamics
PK	Pharmacokinetics
SAE	Serious adverse event
SIOPEN	International Society of Paediatric Oncology Europe Neuroblastoma
Sponsor	Nova Laboratories Limited
SUSAR	Suspected unexpected serious adverse reaction
TEAE	Treatment emergent adverse event
t ½	The terminal half-life of the drug in plasma
VAS	Visual Analogue Scale
V / F	Apparent central compartment volume of distribution
WHO	World Health Organisation

## 1. INTRODUCTION

### **The need for a liquid formulation**

Neuroblastoma (NBL) is an aggressive cancer that predominantly affects children aged 5 years or less. It is an orphan disease (incidence ~ 10 cases per million children; 1 case per 500,000 general population) that still has poor outcomes.

Children who present with metastatic NBL (approximately 50% of cases) are most commonly treated with myelo-ablative chemotherapy followed by stem-cell rescue and, to eradicate 'minimal residual disease' post rescue, 13-cis-retinoic acid (13-CRA, isotretinoin) usually alongside immunotherapy. Given by the enteral route, at a dose of 80 mg/m^2 twice daily, in 2-week cycles for 6 months 13-CRA has been shown in clinical trials to improve event-free survival. Thus, most clinicians accept 13-CRA as frontline therapy for patients with NBL in remission.

However, 13-CRA is not licensed for NBL in any region or country in the world and is currently available only as a gelatin capsule that children are often unwilling and / or unable to swallow. Presently, carers have to 'open' capsules of 13-CRA, and squeeze the contents into foods. As few young children will take capsules, carers often have to administer 13-CRA by first extracting liquid out of the capsule. Studies show that the current method of administration results in marked variability in drug exposure between patients and significantly lower plasma concentrations in patients receiving the extracted drug as compared to those able to swallow the capsules whole (1). Furthermore, since 13-CRA can cause birth defects, pregnant women (e.g. parent of a child with NBL) risk accidentally exposing their unborn babies when extracting 13-CRA from capsules.

No manufacturer has yet developed a child-friendly preparation of 13-CRA. Nova Laboratories Limited is developing a new oral liquid dosage form of 13-CRA, which will facilitate more consistent and accurate dosing and improve palatability for children.

This trial aims to investigate the relative bioavailability and comparative pharmacokinetics of the new oral liquid and existing capsule formulations of 13-CRA in patients. Any patient requiring at least two treatment cycles with 13-CRA will be eligible for the trial. The local oropharyngeal tolerability, the palatability and acceptability of the formulation will also be assessed.

The trial will be conducted in compliance with the protocol, ICH GCP and the applicable regulatory requirement(s).

### **Liquid formulation of 13-cis-retinoic acid**

13-CRA is a derivative of vitamin A. It induces differentiation and growth arrest of malignant NBL cells *in vitro* through binding to retinoid acid receptors and altered gene transcription (2). Currently, the only licensed formulation of 13-CRA is a gelatin capsule with an indication for severe acne.

In patients with NBL the optimal therapeutic blood level for 13-CRA is thought to lie between 2-10 µM (3,4,5). At blood concentrations above 10µM, there is an increased frequency of toxicity reactions (6). Studies indicate that children able to chew and / or swallow 13-CRA capsules are significantly more likely to achieve target concentrations than those who have the drug extracted from capsules prior to administration. Hence, 'method of administration' is a key factor in achieving adequate blood levels of 13-CRA. Since dosing with 13-CRA is not adjusted according to blood levels, inherent variability in dose delivery associated with extracting drug from capsule runs the risk of under- and over- dosing of drug (1). A child appropriate oral liquid formulation of 13-CRA should reduce inter- and intra- patient variability in blood 13-CRA levels

currently seen in patients dosed using the “drug extraction method”. Since 13-CRA is a known teratogen, women of childbearing age are required to have a negative no more than seven days test prior to starting 13-CRA and use of effective contraception during therapy and for 3 months after cessation of treatment. The oral liquid product will also not pose the same level of teratogenic risk for mothers who currently have to extract drug from capsules. Hence, an oral liquid 13-CRA formulation for enteral use would be flexible and child- and carer- friendly. It would also allow for dosing by oral and naso-gastric routes.

### **Benefits and Risks**

The importance and potential benefits of this work to parents, carers and healthcare professionals is clear. The burden of accurately dosing and administering 13-CRA extracted from capsules can only really be described by those intimately involved in this practice. Many healthcare professionals would struggle to perform this task even under ideal conditions.

Any risks associated with taking blood samples from the central line for pharmacokinetic analysis are minimised by following the established aseptic guidelines practiced by the paediatric oncology unit. The number of pharmacokinetic blood samples have been minimised by utilising a sparse sampling population pharmacokinetic modelling approach. However, if the number of samples does cause disruption or irritation to the patient, the patient may be withdrawn from the trial.

### **Justification for the route of administration, dosage and treatment period**

#### ***1.1.1. Route***

13-CRA is administered during the remission phase in the treatment of HRNBL between cycles of immunotherapy and also in patients with unresectable, intermediate risk neuroblastoma with unfavourable INPC histology and in patients with relapsed and refractory disease who have not already received 13-CRA. It is administered orally, currently using the capsule form licensed for severe acne.

It is clear that many young children will not take solid medicines (tablets, capsules). Potential solutions to this issue include developing a liquid for parenteral use, a medicine to be administered by the rectal route and a transdermal drug. While there are other potential solutions, the oral liquid preparation meets important criteria for this medicine including flexible dosing, ease of use, minimal additional risk to patient and carer and patient comfort.

#### ***1.1.2. Dosage***

The dose administered is in accordance with approved practice for 13-CRA extracted capsules. This is based on previous studies have shown that the dose obtained from extracted capsules needs to be adjusted to  $200\text{mg}/\text{m}^2/\text{day}$  in order to achieve the same blood level as that seen for capsules that have been swallowed whole (1). Therefore the dose used in this trial will be  $200\text{mg}/\text{m}^2/\text{day}$  for both test and reference product. Patients with a body weight of  $\leq 12\text{kg}$  will receive a dose of  $160\text{ mg}/\text{m}^2$ .

Patients with HRNBL may be included in the European SIOPEN HRNBL trial (7), which includes treatment with 13-CRA during the maintenance phase. These patients will be excluded from the **My-CRA** trial in order to ensure that the trial endpoints for the SIOPEN clinical trial are not compromised. Patients who are ineligible for the SIOPEN high risk trial, have exited the SIOPEN trial, or patients  $\geq 18$  months with unresectable, intermediate risk neuroblastoma with unfavourable INPC histology who may benefit from at least two cycles of 13-CRA will be dosed according to the currently approved local guidelines.

### **1.1.3. Treatment period**

All patients requiring 13-CRA therapy, who are unable to swallow 13-CRA capsules, will be eligible for recruitment into the trial.

The pharmacokinetics of 13-CRA liquid (test product) and extracted capsule (reference product) will be evaluated in over a two month period to allow for two cycles of treatment in a cross over design (one test treatment period and one reference treatment period). The 14-day treatment period and two week break between treatment cycles is based upon previous studies (7) and is the standard treatment period for cycles of 13-CRA. If patients require a longer period of time between treatments then this will be acceptable within the visit windows (i.e. treatment period 2 will be within 14 +up to 7 days of completion of treatment period 1).

Prior to the initiation of the trial 13-CRA, patients will be randomised to receive either liquid or extracted capsule formulation in “My –CRA month 1”. The patients will then cross-over to the alternative formulation in “My-CRA month 2”. After the trial if a patient requires additional cycles of 13-CRA, the patient will revert to standard 13-CRA therapy i.e. extracted capsules according to local practice.

## **2. AIM AND OBJECTIVES**

The aim of this trial is to investigate the pharmacokinetics, safety, tolerability and palatability of oral liquid 13-CRA in patients aged from 0 months – < 21 years.

### **2.1 Primary objective**

- To determine the relative bioavailability and pharmacokinetics of 13-CRA administered as oral liquid and extracted capsule formulations.

### **2.2 Secondary objectives**

- To determine the safety and tolerability.
- To assess palatability and acceptability.

## **3. TRIAL DESIGN**

### **3.1 Exit points**

The normal exit point from this trial will be when the patient completes the follow up of the second treatment period, i.e. when the patient returns to clinic for their next treatment course or for their next clinic review (it is anticipated that this will be approximately two to three weeks following 13-CRA treatment), all adverse events will be followed up to conclusion.

All patients who have at least one blood sample taken for the pharmacokinetic trial will be included in the population pharmacokinetic analysis. If the parent(s)/legal guardian or patient refuses further blood sampling the patient will be withdrawn from the trial.

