When an appointment is made for the patient to attend the hospital clinic for initiation of 13-CRA treatment the parent(s)/legal guardian of the patient will be approached to discuss the pharmacokinetic trial and the possibility of the patient's entry into the trial; information regarding the trial may be sent to parents and patients prior to them attending. The parent(s)/legal guardian's consent to take these additional blood samples and record physiological information (local [oro-pharyngeal] tolerability, skin toxicity, adverse events) will be sought. Following parental consent, the patient will be approached and the trial procedures explained to them in order to receive their verbal and/or written assent to participate in the trial, if applicable (usually where the patient is over 7 years of age). Parents and patients may still refuse to participate in the trial at any stage prior to or during their treatment with 13-CRA. Parents and patients will be given as much time as they need to consider participation in the trial. Patients and parents may choose to share information about the research with their family or GP before they decide if they would like to take part in the trial. Investigators will ensure that families have at least 24 hours to consider involvement in the trial. In practice this is likely to be longer as parents and patients are most likely to be approached well in advance of their 13-CRA treatment period. If the parent(s)/legal guardian decide that they would not like their patient to participate in the trial then this will in no way affect the onward care of the patient.

When the patient attends hospital for initiation of 13-CRA treatment, it is anticipated that they will have a central line *in situ*. Patients will attend the clinic on Pharmacokinetic days; these will be Day 1 and Day 14 for each of the trial treatment periods. Blood samples for pharmacokinetic analysis will be taken over the course of six hours after which the patients will leave the clinic. Parents and patients will be asked if they are willing to return for an additional sample at 24-48 hours following their final dose on Day 14 of treatment.

Additional assessments will be made according to the trial procedures (section 4).

[figure not shown]
A trial schedule is presented in Appendix I.

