#### 4.6 13-CRA Dosing and Blood sampling for Pharmacokinetic analyses

All patients recruited into the trial will already have a central line *in situ*.

Patients will receive their first morning dose of 13-CRA according to standard practice (for capsules by extracting the medicine from the capsule), or according to liquid dosing instructions, and will include a drink of water (volume to be included in dosing instructions) after dosing. Dosing instructions (including which foods such as yogurt or ice cream can be given with the medicine) for both medicine extracted from capsules and liquid will be provided to the site in a separate dosing manual, this document will be version controlled and retained in the trial files at site.

The pharmacokinetic profile of 13-CRA post dosing will be evaluated.

At least five blood samples (2ml) will be (where possible) taken post-dose at the time-points specified in Table 4.6 below. In patients under two years of age, up to three samples at appropriate sampling times will be taken. Sampling times in the patients under 2 years of age will be discussed with the Sponsor prior to the trial PK sampling days in order to ensure an even spread of sampling times in this younger population of patients. Arrangements will be discussed and agreed in writing (or by email) on an individual basis for this group.

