**Table 4.6 Blood Sampling Schedule**

Time point (h)	Requirements
0.5 (Day 1 and Day 14)	*Two and six hour samples are mandatory.  At least three further samples will be selected over 0.5 to 5 hours (where possible).  **Sample at 24-48 hours applies only to the final dose administered on Day 14 to allow the elimination phase of parent and metabolite(s) to be calculated. For individual patients sampling times should remain the same across each of the four PK days, where possible.
1	
1.5	
2	
3	
4	
5	
6	
24-48 (Day 15 or 16)	

Flushing of the central line with normal saline and allowance for dead space will be performed according to local practice.

2.0 ml blood samples will be taken and processed immediately according to the technical manual and laboratory kit provided to the trial staff. This technical manual will be version controlled and retained in the trial files at site

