11.4 Concomitant Medications

Concomitant medications recorded during the study will be coded using eMIMS. Details of concomitant medication will be listed.

Concomitant medications will be summarized according to whether they were being taken pre-study (prior medications) and/or during the study (concomitant). Prior medications are any that were being taken prior to the first dose of study medication (medication stop date prior to the first dose of study medication). Concomitant medications are any that were being taken on or after the first dose of study medication. If the start and stop dates of the concomitant medications do not clearly define the period during which a medication was taken, it will be assumed to be a concomitant medication.

Prior and concomitant medications will be summarized by treatment sequence, system class and sub-class.

12 Pharmacokinetic Assessments

The population PK analysis detailed in the protocol is not within the scope of this SAP.

Blood samples for measurement of 13-CRA and its metabolite 4-oxo-13-cis-RA will be obtained over the course of 6 hours after each dose. An additional sample 24-48 hours after day 14 will be obtained if possible.

Plasma concentrations will be expressed in ng/mL. All concentrations below the limit of quantification or missing data will be labelled as such in the concentration data listings. Concentrations below the limit of quantification will be treated as zero in summary statistics. Plasma concentrations will be listed and summarised by treatment group, day, and nominal time. In addition, individual plasma concentration-time plots, and mean plasma concentration-time plots by dose will be provided.

PK parameters will be listed. Additionally, PK parameters will be summarised by treatment group and day.

13 Safety

Safety will be assessed from records of adverse events (AEs), oro-pharyngeal tolerability, vital signs and results of physical examination.

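### Protocol 3.1 ends all trial participation when a family refuses further blood sampling, which stops data collection that needs no PK blood and conflicts with other sections

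*Protocol*

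**What the plan says.** **Refusal.** Protocol 3.1: "If the parent(s)/legal guardian or patient refuses further blood sampling the patient will be withdrawn from the trial". The sentence before it puts every patient with at least one sample into the population PK analysis.

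**Burden.** Protocol section 1, Benefits and Risks: "if the number of samples does cause disruption or irritation to the patient, the patient may be withdrawn from the trial".

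**Withdrawal lists.** Protocol 5.3 and the synopsis list a positive pregnancy test, the patient's request and the investigator's discretion. Protocol 8.1 lists withdrawn consent, adverse event, protocol deviation and an open category for other reasons. Neither list names refusal of sampling.

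**Which samples can be declined.** Table 4.6: "Two and six hour samples are mandatory". The three or more further samples per PK day are to be taken only where that is feasible. For the late sample, Protocol 3.2 says: "Parents and patients will be asked if they are willing to return for an additional sample at 24-48 hours following their final dose". SAP section 12 says: "An additional sample 24-48 hours after day 14 will be obtained if possible". For the youngest, Protocol 4.6 says: "In patients under two years of age, up to three samples at appropriate sampling times will be taken".

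**Who is analysed.** Protocol 8.3 takes anyone with one PK sample into the PK analyses. Protocol 11.3.1 and SAP 9.1 limit the PK population to patients who also finish the trial. Protocol 8.3 defines finishing as reaching the end of the 14-day follow-up after Month 2.

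**After withdrawal.** Data up to that point are used unless the family objects (8.1). Adverse events may be followed for up to 14 days (Appendix I, footnote 7). Withdrawn patients may be replaced while fewer than 150 samples have been collected (8.1).

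**The concern.** The secondary objectives are safety, tolerability, palatability and acceptability. The diary, the oro-pharyngeal and skin scores and the Day 14 survey need no PK blood. Yet no section lets a family stop PK sampling and continue these assessments. Under 3.1, refusal before Month 2 removes the whole second-period record, and with it the patient's own comparison of the two formulations.

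The rule is also not applied consistently across the documents. Withdrawal is compulsory in one place, discretionary for a closely related situation in another, and absent from both lists that a site would consult. Nothing says at what point declining samples becomes refusal of further sampling.

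Finally, the two definitions of who enters the PK analysis disagree for exactly these patients. One keeps the samples they gave and the other leaves them out.

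**Working it through.** The plan has no power calculation, refusal rate or dropout rate. The check is therefore a side-by-side reading plus simple counts.

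**1. Follow one patient through the text.** Take a patient who completes Month 1 Day 14 and whose family then refuses all further sampling.

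- Protocol 3.1: must be withdrawn.
- Benefits and Risks: may be withdrawn, if the samples cause disruption or irritation.
- Protocol 5.3 and 8.1: not a named reason. It would have to be treated as the patient's request, investigator discretion or other.
- Protocol 3.1 and 8.3: the samples given stay in the PK analysis.
- Protocol 11.3.1 and SAP 9.1: the patient has not finished the trial, so is outside the PK population. That population feeds SAP Tables 14.2.1 to 14.2.3 and Figures 14.2.4 to 14.2.7.

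**2. Samples already given that step 1 puts in doubt.** Month 1 has two PK days. At five samples per day (age 2 and over): 2 × 5 = 10, or 11 with the late sample. Under age 2, three per day is a ceiling: 2 × 3 = at most 6. The documents do not say whether the late sample is extra for this group.

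**3. Paired non-PK records lost per refusal before Month 2.** Formula: share lost = 1/n. Inputs: at most 20 patients (Protocol 11.3.2), 12 to 18 hoped for (Protocol 11, SAP 7.1).

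- n = 20: 1/20 = 5.0%
- n = 18: 1/18 = 5.6%
- n = 12: 1/12 = 8.3%

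**4. Dependence on timing.** Refusal before Month 1 Day 14 also loses the Month 1 survey. Refusal between the two periods loses all of Month 2. Refusal during Month 2 loses only what remains, and after Month 2 Day 14 little beyond follow-up.

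**5. Does the replacement rule restore the pairs?** It depends on the total of 150 samples, not on completed cross-overs. At five samples per PK day in patients aged 2 and over, Month 1 alone gives 10 per patient, so 150/10 = 15 patients reach the target with no second period. With 12 patients it gives 12 × 10 = 120, below target. In principle, then, the target can be met while lost pairs go unreplaced.

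**6. Does the 150 target need the withdrawal rule?** No. At full sampling over four PK days, a patient aged 2 or over gives 4 × 5 = 20 samples, and 12 such patients give 240. The target counts samples, and a patient who stays only for non-PK assessments leaves that count unchanged.

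**The case against.** The strongest defence is that this is a PK trial. The only primary objective is PK, consent is sought for the additional blood samples, and the inclusion criteria require assent to PK sampling where applicable. A family that refuses all sampling has withdrawn much of what it agreed to. Whether a child should keep receiving a trial product without contributing primary data is an ethical and clinical judgement. That stands, and it is why the treatment consequence belongs to the sponsor and investigators. It does not explain why adverse event, tolerability and survey data must stop too.

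It is also fair to say that the two rules have different triggers (refusal in one, irritation in the other) and that 5.3 and 8.1 are open enough to cover refusal. The sections can thus be read together, but only by a site that chooses to do so.

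A reader might infer that one refused draw, or declining the Day 15/16 visit, forces withdrawal. The documents do not support that. The trigger is refusal of further sampling, a no to an invitation is a foreseen answer, and missed samples beyond 2 h and 6 h are tolerated. Nor are all samples optional, since those two are mandatory.

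Some mitigation stands as well. Data up to withdrawal are kept, the safety population includes non-completers, and adverse events may be followed for up to 14 days. Preference is not always lost: a patient already on extracted capsules before entry and randomised to liquid first could compare both products at Month 1 Day 14.

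**Conclusion.** The point holds as an inconsistency with an avoidable loss of data. Taken literally, Protocol 3.1 ends non-PK collection because PK sampling was refused, and the completion requirement can then exclude samples that Protocol 3.1 and 8.3 say are included.

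The size is 5.0% to 8.3% of paired non-PK records per refusal before Month 2. This assumes 12 to 20 patients and that the whole second period is lost. A reader might want a total, for example 10% to 25% from two or three refusals (2/20 to 3/12). The documents give no refusal rate, so that total has no basis in them. They also give no ground for saying that the youngest or most distressed children would be the ones lost. Under-2s have a reduced schedule agreed individually, and samples come from a central line already in place.

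How much a rewording recovers depends on what the sponsor and investigators decide about treatment after refusal. Without exposure to the second formulation there is no paired record to collect.

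**What to change.** - **Protocol 3.1:** state that refusal of further PK sampling ends PK sampling but does not by itself end collection of non-PK data (adverse events, oro-pharyngeal tolerability, palatability, preference), unless consent to the trial is withdrawn.
- **Protocol 3.2 and Table 4.6:** state that declining the 24-48 h sample is not refusal of further sampling.
- **Protocol 11.3.1 and SAP 9.1:** keep samples already given in the PK analysis, in line with Protocol 3.1 and 8.3.
- **CRF:** record *PK sampling stopped* separately from *withdrawn from trial*.
- **Reconcile** Benefits and Risks, 3.1, 3.2, 4.6, 5.3, 8.1, 8.3 and 11.3.1 of the protocol with SAP 9.1. The sponsor and investigators should state there what refused sampling means for trial treatment; this review does not propose an answer.

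The cost is a few sentences and one CRF field. The small downside is that some patients stay under trial follow-up without giving further PK data.
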